3.1.1. Screening

Following completion of informed consent procedures, subjects will enter the Screening phase of the study.

One to two Screening visits are planned, during which safety screening measures will be undertaken, a practice NTB will be performed, and the required diagnosis and cognitive impairment will be confirmed. Screening will be conducted within 21 days before Baseline (Day 1). If a DaTscanTM is required to determine study eligibility, Screening may be extended to 35 days.

3.1.2. Treatment Period

Once eligibility is confirmed during the Screening period and before the first dose of study drug, subjects will be randomly assigned on a 1:1 basis to placebo or neflamapimod for the 16-week treatment period. Investigators and subjects will be blinded to the treatment assignment. Randomization will be stratified by ISLT Total Recall score at Baseline ($\leq 21 \text{ vs.} > 21$), i.e. by wheter patients have an episodic memory defect at baseline or not.

Subjects will receive study drug for 16 weeks. Dosing will start on Day 1 following completion of all baseline procedures. During the 16-week treatment period, subjects will return to the clinic every 2 weeks for the first month and then every 4 weeks thereafter. A Follow-Up will be conducted 2 weeks (±3 days) after completion of study drug or after the Early Termination visit.

The NTB, ISLT, and NPI-10 will be conducted at Screening, Baseline (Day 1), Week 4 (Day 28), Week 8 (Day 56), and Week 16 (Day 112) or ET if early termination. The CDR-SB and TUG will be conducted at Baseline (Day 1), Week 8 (Day 56), and Week 16 (Day 112) or ET. The MMSE will be conducted at Screening, Baseline (Day 1), Week 8 (Day 56), and Week 16 (Day 112) or ET. EEGs will be conducted at Baseline (Day 1) and Week 16 (Day 112) or ET. Samples for plasma biomarkers will be obtained at Screening, Baseline (Day 1) and Week 16 (Day 112).

3.1.3. Early Termination (ET)

Subjects who prematurely discontinue study drug for any reason will be asked to return to the clinic for an Early Termination (ET) visit within 3 days following the last study drug dose; if it is determined that the subject will discontinue study drug while at the study center for a scheduled visit, then the ET visit should

be conducted at that time. These subjects will also be asked to return to the clinic for a Follow-up Visit 2 weeks (± 3 days) following the last study drug dose.

Every effort should be made to ensure a subject returns for this visit.

Refer to Section 4.3 for details regarding removal of subjects from treatment.

3.2. Discussion of Study Design

Several design features are employed to minimize bias, including the study being double-blind, placebo-controlled, randomized, and multi-centered. The use of placebo control permits blinded prospective comparison between treatment groups. Random assignment of subjects to study treatment avoids bias and helps support both known and unknown risk factors being distributed evenly between treatment groups. Furthermore, randomization is stratified by ISLT Total Recall score at Baseline ($\leq 21 \text{ vs.} > 21$; i.e. by wheter patients have an episodic memory defect at baseline or not) to further balance characteristics of subjects receiving neflamapimod versus placebo. The multi-center nature of the study provides assurance that the results are likely to have general applicability.

3.2.1. Rationale for Dose Selection

3.2.1.1. Efficacy Considerations

The 40 mg BID regimen was initially chosen as the most likely active dose for the prior Phase 2a clinical studies in AD based on the results of the effects of neflamapimod on hippocampal synaptic dysfunction (assessed in the MWM test) in aged rats, which demonstrated that the optimal dose in aged rats was 1.5 mg/kg. The 1.5 mg/kg dose was then correlated to dose-response in rat arthritis models and in human clinical studies in rheumatoid arthritis to derive the predicted dose of 40 mg BID. Furthermore, plasma drug levels obtained in the aged rat at 1.5 mg/kg correspond to those that were seen subjects with AD at 40 mg BID. The predicted cognitive effect at 40 mg BID has been preliminarily demonstrated in humans, as there were statistically significant improvement from baseline in tests of episodic memory function in both phase 2a clinicals studies utilizing this dose. As well there was evidence of target engagement and pharmacological activity at this dose level in the two phase 2a studies, i.e., reductions in amyloid plaque load by PET scan and reductions in interleukin-8 levels in CSF, respectively.

Interim pharmacokinetic results from a Phase 2b clinical study in early AD indicate the median 12-hour plasma drug concentration exposure of neflamapimod in the minority of subjects who weigh ≥ 80 kg is approximately 33% lower that seen in subjects who weigh < 80 kg. The median 12-hour plasma drug exposure was 65 ng*hr/mL in subjects weighing 80 kg or more, and 98 ng*hr/mL in those weighing less than 80 kg. As a higher proportion of subjects with DLB compared to AD are male, and therefore a higher proportion of subjects are expected to weigh ≥ 80 kg, to achieve consistent target plasma drug concentrations in the current study subjects who weigh ≥ 80 kg will receive 40 mg TID (i.e., 120 mg per day, rather than 80 mg per day) of neflamapimod. The median 12-hour plasma drug concentration exposure by utilizing this approach is expected to be approximately 100 ng*hr/mL (i.e., 0.1 µg*hr/mL).

3.2.1.2. Safety Considerations

Based on the clinical experience to date at higher doses and the results from animal toxicology studies, the neflamapimod doses of 40 mg BID in those weighing <80 kg and 40 mg TID in those weighing ≥80 kg is expected to be well tolerated and to have a low risk of drug toxicity.

Dose-limiting toxicity in clinical studies, defined as elevations in liver transaminase levels, was noted in 6 patients of 44 subjects (14%) with RA treated with neflamapimod 250 mg BID (a dose level that achieved median 12-hours plasma drug concentration exposure of 453 ng*hr/mL); 3 of the 6 subjects with transaminase elevations were discontinued prematurely from treatment due to these findings. Patients were asymptomatic, there were no associated increases in bilirubin, and the elevations resolved with treatment discontinuation.

In the Phase 2a studies (Study 303) of 6- or 12-weeks neflamapimod dosing in patients with early AD, a total of 25 subjects were enrolled. With regard to safety, neflamapimod was well tolerated, with 24 of 25 subjects completing their scheduled dosing period (8 completed 6 weeks of neflamapimod administration, and 16 completed 12 weeks of neflamapimod administration). The one subject who discontinued early did so within the first week of study drug administration due to an AE of vomiting, attributed primarily to persistent CSF leakage after the predose/baseline CSF collection. There were no severe or serious AEs reported. The most common AEs across the 2 studies were mild somnolence (sleepiness or drowsiness) reported in 5 patients, and self-limiting mild diarrhea (loose stools) reported in 4 patients. There was also one event of moderate diarrhea, which was considered not related, as the event did not recur during additional 8 weeks of treatment after having resolved during a brief treatment interruption. No treatment-related or clinically relevant trends in the analysis of safety laboratory and 12lead electrocardiogram (ECG) parameters were observed. More specifically, there were no abnormalities in LFTs nor any trends in changes in LFT parameters noted in either study. LFT abnormalities, specifically increases in liver transaminases, were seen in 10% to 15% of patients in a prior study in patients with RA at a dose of 250 mg BID for 3 months. Due to the use of higher doses and different formulations in the RA studies, the plasma drug concentrations were 4- to 5-fold higher than in the Phase 2a mild AD studies.

A Phase 2b study of neflamapimod in early AD (MMSE 20 to 28) is ongoing. A total of 161 patients have been randomized on a blinded basis to either placebo or 40 mg capsules BID with food for 24 weeks. As of November 12, 2018, the annual data safety cutoff date, blinded data were available for 101 patients. As of that date, a total of 70 AEs had been reported across 43 patients. There were two SAEs reported, one a severe unrelated hypokalemia and the other a mild, possibly related non-cardiac chest pain. With the exception of the case of severe hypokalemia, all other AEs were mild to moderate in nature and primarily unrelated. The events deemed at least possibly related and reported more than once include rash, thrombocytopenia, headache, anxiety and lethargy (each reported twice). This study is ongoing and all data are blinded.

The expected plasma drug concentrations in the current study provides a 5-fold margin based on plasma drug levels to no adverse effect level in long term animal toxicity studies and 10-fold margin to minimal and/or equivocal findings for hematological, hepatic and neuropathological changes (evidence of axonal damage) in chronic (9- and 12-month) dog toxicology studies. Further details are provided in the Investigator Brochure (IB).

4. SELECTION OF STUDY POPULATION

4.1. Inclusion Criteria

Subjects meeting all of the following criteria are eligible for enrollment in this study:

- 1. Men and women aged \geq 55 years.
- 2. Subject or subject's legally authorized representative is willing and able to provide written informed consent.
- 3. Probable DLB and identified cognitive deficits, according to current consensus criteria (McKeith et al, 2017), specifically one core clinical feature and a positive DaTscan. If a negative DaTscan, but the subject has historical polysomnography (PSG)-verified REM sleep behavioral disorder (RBD), the subject would also qualify.
- 4. MMSE score of 15-28, inclusive, during Screening.
- 5. Currently receiving cholinesterase inhibitor therapy, having received such therapy for greater than 3 months and on a stable dose for at least 6 weeks at the time of randomization. Except for reducing the dose for tolerability reasons, the dose of cholinesterase inhibitor may not be modified during the study.
- 6. Normal or corrected eye sight and auditory abilities, sufficient to perform all aspects of the cognitive and functional assessments.
- 7. No history of learning difficulties that may interfere with their ability to complete the cognitive tests.
- 8. Must have reliable informant or caregiver.

4.2. Exclusion Criteria

Subjects meeting any of the following criteria are not eligible for enrollment in this study:

- 1. Diagnosis of any other ongoing CNS condition other than DLB, including, but not limited to, post-stroke dementia, vascular dementia, AD, or PD.
- 2. Suicidality, defined as active suicidal thoughts within 6 months before Screening or at Baseline, defined as answering yes to items 4 or 5 on the Columbia-Suicide Severity Rating Scale (C-SSRS), or history of suicide attempt in previous 2 years, or, in the Investigator's opinion, at serious risk of suicide.
- Ongoing major and active psychiatric disorder and/or other concurrent medical condition that, in the opinion of the Investigator, might compromise safety and/or compliance with study requirements.
- 4. Diagnosis of alcohol or drug abuse within the previous 2 years.

- 5. Poorly controlled clinically significant medical illness, such as hypertension (blood pressure >180 mmHg systolic or 100 mmHg diastolic); myocardial infarction within 6 months; uncompensated congestive heart failure or other significant cardiovascular, pulmonary, renal, liver, infectious disease, immune disorder, or metabolic/endocrine disorders or other disease that would interfere with assessment of drug safety.
- 6. Aspartate aminotransferase (AST) or alanine aminotransferase (ALT) > 2 × the upper limit of normal (ULN), total bilirubin > 1.5 × ULN, and/or International Normalized Ratio (INR) > 1.5.
- 7. Known human immunodeficiency virus, hepatitis B, or active hepatitis C virus infection.
- 8. Participated in a study of an investigational drug less than 3 months or 5 half-lives of an investigational drug, whichever is longer, before enrollment in this study.
- 9. History of previous neurosurgery to the brain.
- 10. If male with female partner(s) of child-bearing potential, unwilling or unable to adhere to contraception requirements specified in the protocol.
- 11. If female who has not has not reached menopause >1 year previously or has not had a hysterectomy or bilateral oophorectomy/salpingo-oophorectomy, has a positive pregnancy test result during Screening and/or is unwilling or unable to adhere to the contraception requirements specified in the protocol.

4.3. Removal of Subjects from Treatment

In accordance with the current revision of the Declaration of Helsinki and other applicable regulations, a subject has the right to withdraw from the study at any time and for any reason without prejudice to his or her future medical care by the physician or at the institution. A subject's participation may also be discontinued by the Investigator or Sponsor due to compliance, safety, or other administrative reason (see also Section 6.2.13).

The subject **must** be discontinued from the study for the occurrence of an unacceptable toxicity, including any of the following:

- Any clinically significant infection. (Clinically significant is defined as any infection requiring hospitalization and/or intravenous antibiotics and/or considered to be opportunistic.)
- ALT or AST >8×ULN; ALT or AST >5×ULN for >2 weeks; or ALT or AST >3×ULN and total bilirubin >2×ULN or INR >1.5; or ALT or AST >3×ULN with the appearance of worsening of fatigue, nausea, vomiting, right upper quadrant pain or tenderness, fever, rash, or eosinophilia.

Refer to Section 3.1.3 for details regarding follow-up after early discontinuation. Additional care and treatment will be provided to subjects once study discontinuation, including any required follow-up visits for resolution for study-related AEs, is completed.

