5.6. Dose Modification for Toxicity

No dose modifications are permitted during the study. If a subject is unable to tolerate the assigned study drug dose then the subject should be discontinued from study drug treatment (Section 4.3).

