6. STUDY ASSESSMENTS AND PROCEDURES

6.1. Schedule of Assessments

The schedule of assessments is presented in Table 6-1.

Table 6-1: Schedule of Assessments

	Study Period / Week / Study Day								
								Early	Follow-
	Screening		7	Freatmen	t Period			Termination	Up
	Screening Visit ^a	Baseline	Week 2	Week 4	Week 8	Week 12	Week 16	ET Visit ^e	Follow- Up Visit ^d
Assessment	Within 21- 35 days of D1	D1 ^b	D14	D28	D56	D84	D112	Within 3 days after last dose	Within 14 days (±3) of last dose
Informed Consent	Xe	DI:	(±3)	(±3)	(±5)	(±5)	(±5)		iast dose
	X								
Medical history review	X X ^f								
Pregnancy testing	X						v	v	v
Physical examination ^g Vital signs ^h	X	X	X	X	X	X	X	X	X
Hematology and	X	X	Λ	X	X	X	X	X	Λ
chemistry ⁱ	Λ	A		Λ	Λ	Λ	Λ	Λ	
Coagulation studies ⁱ	X				X				X
12-lead electrocardiogram ^j	X								
DaTscan TM , if needed	X^k								
CT/MRI	X¹								
C-SSRS	X	X		X	X	X	X	X	
MMSE ^m	X	X			X		X	X	
NTB ^m , International Shopping List Test (ISLT)	X	X		X	X		X	X	
CDR-SB		X			X		X	X	
NPI-10	X	X		X	X		X	X	
Timed Up and Go (TUG)		X			X		X	X	
EEG ⁿ		X					X	X	
Dispense study drug		X	X	X	X	X			
Pharmacokinetic sampling ^o			X	X	X				
Plasma sample for protein biomarker testing ^p	X^q	X					X	X	

	Study Period / Week / Study Day								
	Screening	Treatment Period						Early Termination	Follow- Up
	Screening Visit ^a	Baseline	Week 2	Week 4	Week 8	Week	Week 16	ET Visit ^e	Follow- Up Visit ^d
	Within 21-							Within 3 days after	Within 14 days
Assessment	35 days of D1	D1 ^b	D14 (±3)	D28 (±3)	D56 (±5)	D84 (±5)	D112 (±5)	last dose	(±3) of last dose
Prior/concomitant medication	X	X	X	X	X	X	X	X	X
Adverse event recording	X	X	X	X	X	X	X	X	X
Final study drug reconciliation							X	X	

CDR-SB: Clinical Dementia Rating Scale – Sum of Boxes; C-SSRS: Columbia-Suicide Rating Scale; CT: Computed tomography; D=day; MMSE: Mini-Mental State Examination; MRI: Magnetic resonance imaging; NPI-10: 10-item Neuropsychiatric Inventory; NTB: Neuropsychological Test Battery.

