6.2.10. Clinical Laboratory Assessments

Blood samples will be collected at the time points specified in Table 6-1 for assessment of routine chemistry and hematology analytes. Additional blood samples will be collected for coagulation studies at the time points specified in Table 6-1.

All samples will be analyzed via a central laboratory.

Table 6-2: Clinical Laboratory Analytes

Serum	Chemistry
Serum	Chemistry

- Albumin
- Alkaline phosphatase
- ALT
- AST
- Bilirubin (total and direct)
- Glucose
- Blood urea nitrogen
- Calcium
- Bicarbonate/Carbon Dioxide
- Chloride
- Total cholesterol
- Triglycerides
- Creatinine
- Gamma-glutamyl transferase
- Lactate dehydrogenase
- Phosphate
- Potassium
- Sodium
- Total protein
- Uric acid

Hematology

- Differential (absolute and percent)
- Basophils
- Eosinophils
- Lymphocytes
- Monocytes
- Neutrophils
- Erythrocytes
- Mean corpuscular hemoglobin
- Mean corpuscular hemoglobin concentration
- Mean corpuscular volume
- Hemoglobin
- Leukocytes
- Platelets

Coagulation Studies

- Prothrombin time
- Partial thromboplastin time
- INR

Clinical laboratory findings that represent a worsening from Baseline value and are considered by the Investigator to be clinically significant will be recorded as an AE (refer to Section 7).

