6.2.13. Withdrawal of Subjects

A subject may be discontinued from study treatment at any time if the subject, the Investigator, or the Sponsor feels that it is not in the subject's best interest to continue. The following is a list of possible reasons for study treatment discontinuation:

- Subject withdrawal of consent (or withdrawal of surrogate consent)
- Subject develops suicidal ideations or attempts suicide
- Subject is not compliant with study procedures
- AE that in the opinion of the Investigator would be in the best interest of the subject to discontinue study treatment
- Protocol violation requiring discontinuation of study treatment
- Lost to follow-up
- Sponsor request for early termination of study

If a subject is withdrawn from treatment due to an AE, the subject will be followed and treated by the Investigator until the abnormal parameter or symptom has resolved or stabilized.

A subject may be withdrawn from the study at any time if the subject, the Investigator, or the Sponsor feels that it is not in the subject's best interest to continue.

All subjects are free to withdraw from participation at any time, for any reason, specified or unspecified, and without prejudice.

Reasonable attempts will be made by the Investigator to provide a reason for subject withdrawals. The reason for the subject's withdrawal from the study will be specified in the subject's source documents.

Refer to Table 6-1 for assessments to be performed for subjects who prematurely discontinue study drug.

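### The mandatory two-week stopping rule for ALT or AST above 5×ULN cannot be applied on time from the required chemistry samples, which from Week 4 are four weeks apart with no repeat required

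*Protocol*

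**What the plan says.** Section 4.3 states that a subject must be discontinued "for the occurrence of an unacceptable toxicity, including any of the following". One item in the list is "ALT or AST >5×ULN for >2 weeks". The same bullet has limbs that can be judged at a single visit: ALT or AST above 8×ULN, or above 3×ULN together with raised bilirubin or INR, or with listed symptoms or eosinophilia.

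Section 3.1.2 sets the visit pattern: "subjects will return to the clinic every 2 weeks for the first month and then every 4 weeks thereafter". Section 6.2.10 ties the laboratory work to that schedule: "Blood samples will be collected at the time points specified in Table 6-1 for assessment of routine chemistry and hematology analytes". In Table 6-1 the chemistry row is marked, from Week 4 on, at Weeks 4, 8, 12 and 16 and at early termination.

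On managing a subject who stays on treatment, Section 5.6 says "No dose modifications are permitted during the study" and adds that a subject who cannot tolerate the dose should come off study drug. Section 4.3 also allows a discretionary stop ("participation may also be discontinued by the Investigator or Sponsor due to compliance, safety, or other administrative reason"). Section 6.2.13 lists among the reasons for stopping an "AE that in the opinion of the Investigator would be in the best interest of the subject to discontinue study treatment".

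**The concern.** The rule is compulsory and depends on duration, so it works only if a second sample is taken soon after two weeks. The required schedule provides no such sample, and nothing in the protocol orders one. A site that follows the rule and the schedule to the letter commits no deviation, yet can stop a subject about two weeks later than the protocol's own limit.

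Transaminase elevation is the toxicity that Section 3.2.1.2 calls dose-limiting. In rheumatoid arthritis patients at 250 mg BID, 6 of 44 had elevations and 3 were discontinued. The elevations resolved when treatment stopped, which is the step delayed here. Because the dose may not be changed, a subject who waits for the next visit does so on the full assigned dose.

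**Working it through.** **Inputs.** Visit days and windows from Table 6-1: Week 4 = D28 ±3 (D25 to D31), Week 8 = D56 ±5 (D51 to D61), Week 12 = D84 ±5 (D79 to D89), Week 16 = D112 ±5 (D107 to D117). Duration limit from Section 4.3: more than 14 days. The Week 2 column is not used.

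**Start of the count (assumed).** The protocol does not say when the two weeks begin. I count from the first sample showing a value above 5×ULN. True onset is earlier, so this start is favourable to the plan.

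**Reproducing the stated interval.** 56 − 28 = 84 − 56 = 112 − 84 = 28 days, which agrees with the four-weekly visits in Section 3.1.2.

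**Gap and delay.** Shortest gap = earliest next day − latest current day. Longest gap = latest next day − earliest current day. Delay = gap − 14.

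| First seen → next required sample | Nominal gap | Shortest gap | Longest gap | Delay past two weeks |
|---|---|---|---|---|
| Week 4 → Week 8 | 28 | 51 − 31 = 20 | 61 − 25 = 36 | 14 (6 to 22) |
| Week 8 → Week 12 | 28 | 79 − 61 = 18 | 89 − 51 = 38 | 14 (4 to 24) |
| Week 12 → Week 16 | 28 | 107 − 89 = 18 | 117 − 79 = 38 | 14 (4 to 24) |

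The 24-day extreme needs the first visit 5 days early and the second 5 days late. In the last row the decision coincides with the end of dosing, so the limb cannot shorten treatment.

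**What 14 days means per case.** 14 × 2 = 28 capsules on BID or 14 × 3 = 42 on TID; 14/112 = 12.5% of the course.

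**Effect of a repeat 15 days after the first value.** A sample at exactly 14 days cannot show more than two weeks, so 15 is the first usable day. Days gained = gap − 15: nominal 13; 5 to 21 if first seen at Week 4; 3 to 23 if first seen at Week 8 or 12.

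**Is a repeat required anywhere?**
- Sections 4.3 and 6.2.10 contain no repeat clause.
- Section 7.1.4 mentions diagnostic tests, but only as a criterion for recording a laboratory abnormality as an AE.
- Section 6.2.13 requires follow-up of an abnormal parameter only after withdrawal from treatment for an AE, and sets no interval.
- Section 7.2.2 requires follow-up of SAEs, again without an interval.

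**Likely harm.** The rheumatoid arthritis elevations occurred at a median 12-hour exposure of 453 ng*hr/mL, against about 100 ng*hr/mL expected here (Sections 3.2.1.2 and 3.2.1.1): 453/100 ≈ 4.5-fold.

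**The case against.** The best reply is that a compulsory duration rule implies its own recheck. An investigator holding a value above 5×ULN cannot comply by waiting four weeks, Table 6-1 lists scheduled samples without forbidding others, and Section 7.1.4 shows that testing in response to an abnormal value is contemplated. On this reading the rule and schedule do not conflict, and only operational wording is missing. Part of this stands: investigators may retest or stop early, and many would. But an implied retest has no timing, and a well-meant repeat at exactly two weeks would not satisfy the criterion. Approximately 22 centres would each settle this for themselves.

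The second reply is that few subjects could be affected and little harm is likely. This largely stands. The affected subject has a value above 5 but not above 8×ULN for more than two weeks, no listed symptom or eosinophilia, bilirubin not above 2×ULN, INR not above 1.5, and an investigator who neither retests nor stops. Only about 40 subjects are planned to receive active drug. The rheumatoid arthritis patients were asymptomatic, with no bilirubin rise. The 25 Phase 2a Alzheimer's patients (40 or 125 mg BID) had no liver test abnormality. Blinded Phase 2b data on 101 patients name no liver event among the at least possibly related events reported more than once. Section 3.2.1.2 cites a 5-fold margin to the no adverse effect level and a 10-fold margin to minimal or equivocal hepatic findings in dogs. The capsule counts describe one case, not an expected burden. These points limit the priority of the change but do not make the rule workable as written.

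**Conclusion.** The concern holds. On required samples alone, the limb is decided a nominal 14 days after the two-week point, with a range of 4 to 24 days across the permitted windows. The result rests on two conditions: the count starts at the first value above 5×ULN, and the investigator neither retests nor stops at discretion. The number of subjects affected cannot be estimated, because the protocol does not report how many exceeded 5×ULN in earlier studies. No endpoint or analysis is affected. The change should be made because the rule is mandatory and the correction cheap, not because many subjects are at risk.

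**What to change.** Add to Section 4.3, with a cross-reference in Section 6.2.10: *Any on-treatment ALT or AST above 5×ULN requires a prompt unscheduled repeat of ALT, AST, total bilirubin and INR (for example within one week), and the Medical Monitor is informed. If treatment continues and the value is still above 5×ULN, a further repeat is drawn 15 days after the first such value, or as soon as possible thereafter.*

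The essential element is the 15-day repeat; the one-week repeat and the Medical Monitor notice are optional. Bilirubin and INR are included so that the 3×ULN limb can be judged from the same sample. INR must be named, because Table 6-2 lists it under coagulation studies and a chemistry repeat would omit it.

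The cost is two sentences and a cross-reference, plus extra blood samples only when triggered, each with a clinic trip for subject and caregiver. No threshold and no entry in Table 6-1 changes.
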